The primary endpoint of this study will be to determine if therapy with oral divided-dose ACZ administered each day for week-long period results in at least 15% increase in CBF. Studies have shown between 10% - 15% decrease in cerebral perfusion in patients with relapsing MS (Adhya et al., 2006). Therefore, increases in CBF of at least 15% might result in change to lesion evolution. Baseline CBF measures will be compared to measures obtained at each dose escalation step using paired *t* test and Mann-Whitney test.

Determine the effect of long-term oral ACZ on lesion evolution. The key secondary endpoint of this study is to determine if long-term use of oral daily divided-dose with ACZ improves tissue integrity in a proportion of MS lesions.

MRI scans will be segmented using into white and gray matter, T2 and T1 lesion components and contrast-enhancing lesion component. Expert raters (I.V., S.D., L.F.), who are blinded to treatment arm (see section 6.1) will perform quality control of the automated segmentation and obtain quantitative measures of cerebral perfusion. The number and volume of T2 hyperintense and T1 hypointense lesion will be determined using MRIAP. The ratio of T1 hypointense/T2 hyperintense lesion will be determined for baseline and each crossover period and correlated with CBF, CBV and MTT measures obtained at similar times using the Spearman rank correlation.

Diffusion tensor imaging (DTI) is a reliable, validated technique that quantitatively measures molecular diffusivity within tissue and provides information about its microstructural integrity. DTI will be used to monitor tissue integrity and correlate change with increases in CBF following ACZ.

Tertiary Objectives

Several studies have quantitated transverse and longitudinal relaxation times within lesions and normal-appearing white matter and gray matter. These studies have shown that changes in both transverse and longitudinal relaxation can precede lesion formation and possibly better evaluate lesion evolution as compared to black hole volumes (Papadopoulos et al., 2010; van Walderveen et al., 1999a; Walsh et al., 2014; Warntjes et al., 2013). We will manually delineate regions of interest within lesions to obtain T2 and T1 relaxometry metrics. Lesions within areas with greatest change in CBF will be compared with those with least change. We anticipate a correlation between relaxometry measures and areas with varying CBF.

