During the dose escalation, in addition to issues of tolerability, subjects will be monitored at each transition point for the following specific serious AEs: paraesthesia, change in taste, accelerated change in blood pressure or fluid retention. Any subject with serious AEs will be withdrawn from the study. Patients with persistent serious AEs will be treated using standard medical practice.

STUDY POPULATION

List the number of subjects to be enrolled.

This exploratory study is designed to evaluate the long-term effects of oral ACZ on CBF in adult subjects with MS. We will enroll 100 MS subjects between the age of 18 and 55 without history of cerebrovascular disease or glaucoma.

There are several studies suggesting that MS lesions in the pediatric population differ from that typically seen in the adult population (Ghassemi et al., 2014; Renoux et al., 2007). To minimize potential confounding variables, all stages of the study will recruit only adult subjects with MS.

All subjects will be recruited from patients seen at the MS clinic located at the University of Texas Professional building (UTP) Neurology practice

Information about the study will be available on the UT Neurology web site and in print format at the UTP MS clinic.

Informed consent will be obtained from each participant prior to entry and, for subjects who elect to

participate in multiple parts of the study, prior to each stage.

Criteria for Recruitment

Subjects who wish to participate in either stage of the study will be evaluated by the principle investigator to determine if they meet inclusion and exclusion criteria. A thorough medical history will be performed to determine if any pre-existing cardiovascular disease or glaucoma is present. Subjects whose history is unknown will be encouraged to obtain evaluation by a primary care physician and eye-care specialist prior to recruitment. In addition, available blood tests, performed within six months of study entry, will be reviewed to determine if any renal or hepatic dysfunction is present.

Potential subjects with historical or laboratory evidence to suggest dysfunction in one of the above clinical systems will be excluded from study participation. As the rate of these comorbidities is low in a young population, we do not anticipate large numbers of failures at this stage of screening.

Inclusion Criteria

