- 16. Positive pregnancy test or inability or unwillingness to use effective means of birth control. Effective birth control is defined as:
 - Refraining from all acts of vaginal intercourse (abstinence)
 - Consistent use of birth control pills
 - Tubal sterilization or male partner who has undergone vasectomy
 - Placement of an IUD (intrauterine device)
 - Use, with every act of intercourse, of a diaphragm with contraceptive jelly and/or condoms with contraceptive foam
- 17. Presence of metallic objects implanted in the body that would preclude the ability of the subject to safely have MRI exams.
- 18. Psychiatric illness, mental deficiency, or cognitive dysfunction making compliance with treatment or informed consent impossible.

Withdrawal Criteria

Patients can be withdrawn at any time if the investigator concludes that it would be in the patients' best interest for any reason. Patients may voluntarily withdraw from the study for any reason at any time. They may be considered withdrawn if they state an intention to withdraw, or fail to return for visits, or become lost to follow up for any other reason. Protocol violations should not lead to patient withdrawal unless they indicate a significant risk to the patient's safety. If premature patient withdrawal occurs for any reason, the principle investigator must determine the primary reason for a patient's premature withdrawal from the study and record this information on the Unanticipated Problems Tracking Log.

For patients who are lost to follow-up (i.e., those patients whose status is unclear because they fail to appear for study visits without stating an intention to withdrawal), the investigator will show "due diligence" by documenting in the source documents steps taken to contact the patient, e.g., dates of telephone calls, registered letters, etc. In the case of death, a patient will be considered withdrawn.

Subject Replacement

Patients who prematurely withdraw will not be replaced.

TRIAL SCHEDULE

Visit Schedule:

Stage 1a – IV ACZ in MS Subjects											
Total of 10 subjects (5 healthy and 5 MS patients)											
	Day -7	0 min	15 min	30 min	120 min	240 min					
	Screen										
Treatment		1 gm	1 gm IV bolus ACZ administered								
		immedia									
H&P	Х										
CBC, CMP	Х										
Urine pregnancy	Х										
pCASL MRI		Х	Х	Х	Х	Х					
DSC MRI						Х					

Stage 1b –Oral ACZ dose-escalation in MS Subjects											
Up to a Total of 10 subjects											

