Stage 1b - Participants in this stage of the study will be given escalating divided doses of oral ACZ up to 4000 mg per day to determine both the magnitude of change to cerebral perfusion with maintenance daily oral ACZ therapy and to define the optimum dose(s) for additional studies. Stage 1b and 2 of the study will utilize extended release oral ACZ, distributed by Hermann Research pharmacy and self-administered by the subject.

r	500mg BID	1000 mg BID	1500 mg BID	2000 mg BID	_	Legend + MPL pCASI
W -1	w o	W 2	W 4	W 6	W 8	+ MSFC + EDSS
Screening	+	÷	+	+	+	
	±	‡	+ *	+ +	+ *	

Treatment and data collection for stage 1b will take 2.5 months for each enrolled subject. As many as two subjects can be evaluated during the month and we would anticipate that this portion of the study can be completed within twelve months.

Image analysis will be performed once each subject completes treatment. Cerebral perfusion measures will be determined for each dose by the same unblinded analyst (S.D.).

Stage 2a - This stage will continue to gather information about whether daily oral ACZ is tolerated and the kinetics of the treatment effect. Patients continue on the same dose for 12 consecutive weeks and undergo repeat imaging at predetermined intervals. Sustained treatment over a short duration will allow us to rapidly determine whether sustained treatment with ACZ can alter cerebral blood flow and will provide a go/no-go for future studies using this drug/paradigm. Patients will obtain MRI scans and clinical evaluations every 6 weeks with contrast-based scans repeated at 12 weeks.

Stage 2b - This stage will determine long-term tolerability and if tachyphylaxis is present with oral ACZ. Patients will continue on the same dose for 24 consecutive weeks and undergo repeat imaging at predetermined intervals. MRI scans and clinical evaluations will be obtained every 6

weeks with contrast-based scans repeated every 12 weeks.

Stage 3 - This stage is a prospective delayed-start design to evaluate the potential for ACZ to persistently enhance cerebral perfusion and impact the evolution of MS lesions. This pilot study is anticipated to lead to a larger randomized phase 3 clinical trial.

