Caution is advised for patients receiving concomitant high-dose aspirin and acetazolamide, as anorexia, tachypnea, lethargy, metabolic acidosis, coma, and death have been reported.

PRECAUTIONS

General

Increasing the dose does not increase the diuresis and may increase the incidence of drowsiness and/or paresthesia. Increasing the dose often results in a decrease in diuresis. Under certain circumstances, however, very large doses have been given in conjunction with other diuretics in order to secure diuresis in complete refractory failure.

Information for Patients

Adverse reactions common to all sulfonamide derivatives may occur: anaphylaxis, fever, rash (including erythema multiforme, Steven-Johnson syndrome, toxic epidermal necrolysis), crystalluria, renal calculus, bone marrow depression, thrombocytopenic purpura, hemolytic anemia, leukopenia, pancytopenia, and agranulocytosis. Caution is advised for early detection of such reactions and the drug should be discontinued and appropriate therapy instituted.

In patients with pulmonary obstruction or emphysema where alveolar ventilation may be impaired, acetazolamide which may precipitate or aggravate acidosis should be used with caution. Gradual ascent is desirable to try to avoid acute mountain sickness. If rapid ascent is undertaken and acetazolamide is used, it should be noted that such use does not obviate the need for prompt descent if severe forms of high altitude sickness occur, i.e., high altitude pulmonary edema (HAPE) or high altitude cerebral edema.

Caution is advised for patients receiving concomitant high-dose aspirin and acetazolamide, as anorexia, tachypnea, lethargy, metabolic acidosis, coma, and death have been reported (see WARNINGS).

Both increases and decreases in blood glucose have been described in patients treated with acetazolamide. This should be taken into consideration in patients with impaired glucose tolerance or diabetes mellitus.

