In those unusual instances where adequate control is not obtained by the twice-a-day administration of acetazolamide extended-release capsules, the desired control may be established by means of acetazolamide (tablets or parenteral). Use tablets or parenteral in accordance with the more frequent dosage schedules recommended for these dosage forms, such as 250 mg every four hours, or an initial dose of 500 mg followed by 250 mg or 125 mg every four hours, depending on the case in question.

Acute Mountain Sickness:

Dosage is 500 mg to 1000 mg daily, in divided doses using tablets or extended-release capsules as appropriate. In circumstances of rapid ascent, such as in rescue or military operations, the higher dose level of 1000 mg is recommended. It is preferable to initiate dosing 24 to 48 hours before ascent and to continue for 48 hours while at high altitude, or longer as necessary to control symptoms.

HOW SUPPLIED

Acetazolamide Extended-Release Capsules, 500 mg are white to off-white pellets filled in empty hard gelatin capsules with orange opaque cap imprinted with "EP" in black ink and white opaque body imprinted with "107" in black ink and are supplied as follows:

Unit dose packages of 30 (3x10) NDC 68084-401-21

Storage and Drug Accountability

Acetazolamide tablets will be stored at room temperature (between 68°F to 77°F) as suggested by the manufacturer. Intravenous formulation of ACZ will be stored as lyophilized powder at the temperature specified above in the Hermann Research pharmacy. Lyophilized powder will be reconstituted prior to infusion by the pharmacy. All study medication will be stored at the Hermann Research pharmacy and dispensed as needed during study.

TREATMENT

Rationale for Selection of Dose

The ACZ challenge test, using 1000 mg IV ACZ, is a commonly utilized clinical tool in evaluating patients with chronic intracerebral occlusive disease and is a reliable predictor of critically reduced cerebral perfusion (Vagal et al., 2009). Oral doses as high as 4000 mg daily have been previously used in the NORDIC clinical trial (NORDIC Idiopathic Intracranial Hypertension Study Group Writing Committee et al., 2014).

Participants in this study will be treated with the highest tolerated dose of oral ACZ extended release capsules shown to exert the greatest effect on cerebral perfusion. This dose will also be utilized for an anticipated subsequent large phase 3 trial to determine clinical efficacy.

Study Drug Formulations

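### Stage 1b compares each dose step with baseline in whoever was scanned at that step, so if intolerant subjects leave, comparisons across steps can be distorted by selection

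*Combined protocol and SAP*

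**What the plan says.** Under Primary & Key Secondary Objective, the endpoint is whether oral treatment "results in at least 15% increase in CBF". The analysis given for the dose steps is: "Baseline CBF measures will be compared to measures obtained at each dose escalation step using paired" t tests, together with a Mann-Whitney test. The Trial Schedule sets the size of Stage 1b: "Up to a Total of 10 subjects".

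Four other passages bear on who contributes to each test.

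- **Withdrawal.** End Points - Safety removes anyone who cannot tolerate study medication. For listed events checked at each dose transition, including paraesthesia, it adds: "Any subject with serious AEs will be withdrawn from the study".
- **Replacement.** Subject Replacement states: "Patients who prematurely withdraw will not be replaced".
- **Dose and tolerability.** The Precautions in the reproduced oral package insert say that increasing the dose "may increase the incidence of drowsiness and/or paresthesia".
- **Image reading.** Study Design, Stage 1b, states: "Image analysis will be performed once each subject completes treatment".

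On the use of the results, Rationale for Study Design and Study Design both give Stage 1b the task of defining the optimum dose or doses for later work. Rationale for Selection of Dose says participants will receive "the highest tolerated dose of oral ACZ extended release capsules shown to exert the greatest effect on cerebral perfusion".

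**The concern.** A paired test at a given step can use only subjects who have both a baseline scan and a scan at that step. Escalation is sequential, so a subject withdrawn at one dose has no scan at any higher dose. By the plan's own account, tolerability may worsen as the dose rises. The lower steps may therefore describe most of the cohort and the higher steps only those who tolerated everything before.

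Each step's contrast is still a fair summary for the subjects in it. The difficulty comes when steps are set against each other, which any statement about the greatest effect requires. A rise, plateau or fall across steps could then reflect a change in who is being measured rather than in what the drug does. With at most 10 subjects, one withdrawal removes at least a tenth of the cohort from every later step.

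**Working it through.** The plan gives no power calculation, SD or withdrawal rate for Stage 1b, so there is no figure to reproduce. What follows is an illustration.

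**Inputs**

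- 10 subjects: the Stage 1b maximum in the Trial Schedule.
- Four dose steps: the Stage 1b table (the visit narrative has five).
- True gain of 15 points at every step: an assumption. The size matches the plan's 15% target; the flatness makes any apparent trend an artefact.
- SD 30 and within-subject correlation 0.5: from Section 11, where they are stated for Stage 3. Applying them to Stage 1b change from baseline is an assumption.
- Cumulative loss by the last step of 18%, 30% or 50%: assumptions. Only 18% appears in the plan, as Stage 3 dropout.
- Correlation ρ between a subject's intolerance and own CBF response of 0.3 or 0.5: an assumption. The documents give neither its size nor its sign.

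**Bias of the last-step mean**

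The between-subject SD of response is 30 × √0.5 = 21.2. If the most intolerant subjects leave and a proportion p remains, the mean intolerance score of those remaining is −φ(z_p)/p, where z_p is the normal quantile at p and φ the normal density. Hence

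bias = −ρ × 21.2 × φ(z_p)/p.

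| Loss | p | φ(z_p)/p | Bias, ρ = 0.3 | Bias, ρ = 0.5 |
|---|---|---|---|---|
| 18% | 0.82 | 0.262/0.82 = 0.320 | −2.0 | −3.4 |
| 30% | 0.70 | 0.348/0.70 = 0.497 | −3.2 | −5.3 |
| 50% | 0.50 | 0.399/0.50 = 0.798 | −5.1 | −8.5 |

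Simulated cohorts of 10 give −2.0, −3.4 and −5.1 at ρ = 0.3, and −3.4, −5.5 and −8.6 at ρ = 0.5. Against a 15-point gain, the range runs from 2.0/15 = 13% to 8.6/15 = 57%. With ρ = 0 the formula gives zero. With ρ negative, so that poor responders leave, the sign reverses and the size is unchanged.

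**Effect on the apparent dose pattern**

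A separate simulation used a between-subject SD of 20, visit noise SD of 15 and 10% withdrawal per step, again with a flat true gain of 15.

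| ρ | Step 1 | Step 2 | Step 3 | Step 4 | Runs in which step 4 looks best |
|---|---|---|---|---|---|
| +0.5 | 13.1 | 11.6 | 10.5 | 9.4 | 18% |
| 0 | 15.0 | 15.0 | 15.0 | 15.0 | 27% |
| −0.5 | 16.9 | 18.3 | 19.5 | 20.6 | 36% |

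With no withdrawals, each step looks best in 25% of runs. Expected numbers on drug fall as 10 × 0.9^k: 9.0, 8.1, 7.3 and 6.6.

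**What a model on all scans does**

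Where everyone has a first on-drug scan, a mixed model on all available scans leaves a last-step bias of −0.7, −1.4 and −1.8 points at ρ = 0.3, and −1.3, −2.3 and −3.2 at ρ = 0.5. When the correlation is estimated from the data, about 30% to 65% of the bias remains. If loss can precede the first on-drug scan, one scenario goes only from −4.2 to −2.4. In nearly every scenario the root mean square error of the last-minus-first contrast falls, by roughly 2% to 17%. With no tolerability-response link it still falls, by 3%, 5% and 10% for the three loss levels.

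**The case against.** **Bias is not shown to occur.** A reader might infer that the Stage 1b comparison is biased. The documents do not support that. Bias needs withdrawals to happen and tolerability to be related to CBF response. The insert links dose to drowsiness and paresthesia, not to blood flow. This objection stands: the bias is possible and its direction unknown.

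**No test picks the dose.** A reader might also infer that these paired tests select the dose. They compare each step with baseline only; the plan contains no between-dose test and no numerical rule. The Stage 2b text and the Stage 2a table already state 1000 mg twice daily. This also stands, but the plan still asks Stage 1b which dose has the greatest effect, and offers only these contrasts to answer it.

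**Tolerators may be the right group.** If tolerability is part of the choice, the effect among those who tolerate a dose is useful. That supports reporting each contrast beside its counts. It does not make contrasts from different subjects comparable with each other.

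**Section 11 may cover it.** That section declares all analyses intent-to-treat and assigns mixed models to all outcomes. The terms it lists (treatment group, group-by-time interaction, stratifying disease duration) describe randomized Stage 3 and cannot be fitted as written to a single-arm escalation.

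**The image-reading sentence is about timing.** It does not say that scans from withdrawn subjects are discarded, and it should not be read as proof that they are. It is merely silent on subjects who stop early.

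**The size is modest against noise.** At 18% loss, 8.2 subjects are expected at the last step, so its mean has a sampling SD of about 30/√8.2 = 10.5 points, against a bias of 2.0 to 3.4. This is fair, and it is why the change is offered as a cheap improvement.

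**Conclusion.** The point holds in a conditional form. The plan's separate paired tests use only subjects scanned at each step, intolerant subjects leave without replacement, and no Stage 1b analysis handles the missing scans. Comparisons across steps can therefore be biased in either direction if tolerability is related to CBF response, and are unbiased if it is not.

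Under the borrowed Stage 3 variance figures, with 18% to 50% loss and a correlation of 0.3 to 0.5, the last-step mean is off by roughly 2 to 9 points on a 15-point gain. The upper part of that range needs losses well above any rate the plan mentions. Nor can it be assumed that everyone contributes to the first step: its scan comes after two weeks of dosing, so a subject may leave with no on-drug scan.

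**What to change.** For comparing steps, replace the separate tests with one linear mixed model for Stage 1b, with a random subject effect and every available scan from every subject, including those later withdrawn. Two specifications are coherent:

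- log CBF, with baseline and each dose step as categorical levels; or
- change from baseline, with the on-drug steps only.

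Percent change should not be combined with baseline as a level, because it is zero for everyone at baseline.

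For each step, report the estimate with its confidence interval, the number scanned, and the number withdrawn before it, including those lost before any on-drug scan. In Study Design, Stage 1b, state that images are analysed once a subject completes or stops treatment.

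The cost is wording and a little more analysis, with no new subjects, scans or visits. The model assumes that dropout depends on responses already observed, so some bias can remain, and it helps less when subjects leave before any on-drug scan.

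Separately, these passages must be reconciled:

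- the number of dose steps (four in the Stage 1b table, five in the visit narrative);
- the Stage 1b maximum (1500 mg per day in Rationale for Doses Selected, 4000 mg per day in Rationale for Study Design and Study Design);
- the Stage 2 dose (1000 mg twice daily in the Stage 2b text and Stage 2a table, left to Stage 1b in the Stage 2b table).

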The primary aim of the proposed study is to evaluate the change in global CBF with ACZ, so the primary outcome is the change in global CBF after 24 weeks relative to pre-treatment baseline. Based on the preliminary data, we expect to see a 15% difference between the ACZ treatment and placebo groups on the improvement in global cerebral perfusion with standard deviation (SD) of 30%. We ran Monte Carlo simulations under a linear mixed effect model (same model as planned for analysis) and calculated a needed total sample size of n=50 to detect a group difference of 0.5 SD at the 24 weeks (phase 1) assuming a within-subject correlation of 0.5, a significance level of 0.05, and 90% power. We hypothesize a similar group difference in phase 2 (ACZ-ACZ group would not change between weeks 24 and 48 but delayed-start group would improve) and similar power to detect this effect. With 50 patients, for Aim 1.2, we will have 80% power to detect an average correlation as low as 0.39 between CBF and MD or FA. Considering a dropout rate of 18%, we need to recruit 60 participants. Aims 2 are mainly exploratory and parameters derived from this study will be used to help design future larger scale confirmatory studies.

All analyses will be intent-to-treat. To summarize the data, descriptive statistics will be used. Demographics and baseline characteristics at randomization will be summarized for each treatment arm. Generalized linear mixed models will be used to analyze all outcomes and will include treatment group and time, group-by-time interaction, and disease duration (stratifying variable) as covariates, and a random intercept to account for within-patient correlation.

For the primary outcome, we will focus on comparing the treatment groups in phase 1. A linear mixed model will be used to compare the estimated change in global CBF between baseline and week 24 in the ACZ and delayed-start groups. A secondary analysis will study ACZ treatment effect on CBF in different regions by treating regions as clusters in the linear mixed model. If normality of CBF outcome does not hold, an appropriate transformation or different outcome distribution will be used.

For the secondary endpoint at 48 weeks (phase 2), a similar mixed model will be used to compare changes in global CBF between weeks 24 and 48 weeks in the early-start and delayed-start groups. The model will include the same terms as for phase 1.

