Secondary outcomes considers repeated measures of MD or FA at different time in different regions. Linear mixed models will be used to evaluate changes in MD and FA from baseline (24 weeks for delayed-start) to 24 weeks (48 weeks for delayed-start) after ACZ therapy. These changes will be compared between regions with and without increased CBF (>15% difference from baseline). Terms in the model will be as for CBF with the addition of increased CBF (yes/no) for the region. Mixed models will also be used to compare MD and FA changes between white matter areas with and without lesions.

Logistic or linear mixed models will be used to evaluate change from baseline to after 24 week ACZ therapy (using phase 1 and phase 2 data) in the tertiary composite change outcome. Models will include the same terms as for analyses of the primary outcome. We will evaluate associations between changes in clinical outcomes and changes in CBF, CBV, and MTT by including each of these variables (one at a time) as a time-varying covariate.

As this trial uses a small sample size, we would not expect statistically significant treatment effects on clinical disability though this exploratory measure should be useful in power calculation for the anticipated larger, randomized clinical trial.

ETHICAL CONSIDERATIONS

Informed Consent

The informed consent form is a method of providing information regarding the trial to a prospective participant and allows for an informed decision about participation in the study. All participants (or their legally acceptable representative) must read, sign, and date a consent form before participating in the study, taking study drug, and/or undergoing any study-specific procedures. If a participant does not speak and read English, the consent materials will be translated into the Spanish.

The informed consent form will be updated or revised whenever important new safety information is available, whenever the protocol is amended, and/or whenever any new information becomes available that may affect a subject's participation in the trial.

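### The key secondary endpoint is a proportion of MS lesions that improve, but Section 11 analyses MD and FA by undefined region and never estimates that proportion or an explicit randomised effect within lesions

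*Combined protocol and SAP*

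**What the plan says.** Section 2.2 names the endpoint: whether "long-term use of oral daily divided-dose with ACZ improves tissue integrity in a proportion of MS lesions". The Hypothesis section and End Points - Efficacy put the question the same way, as a share of lesions whose tissue integrity improves. The rest of Section 2.2 gives two analyses. One is a lesion ratio: "The ratio of T1 hypointense/T2 hyperintense lesion will be determined for baseline and each crossover period and correlated with CBF, CBV and MTT measures", by Spearman rank correlation. The other is diffusion imaging: "DTI will be used to monitor tissue integrity and correlate change with increases in CBF following ACZ".

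Section 11 is worded differently: "Secondary outcomes considers repeated measures of MD or FA at different time in different regions". Linear mixed models will "evaluate changes in MD and FA from baseline (24 weeks for delayed-start) to 24 weeks (48 weeks for delayed-start) after ACZ therapy". Two comparisons follow: "These changes will be compared between regions with and without increased CBF (>15% difference from baseline)", and "Mixed models will also be used to compare MD and FA changes between white matter areas with and without lesions". Model terms are those used for CBF, plus a yes/no indicator of increased CBF for the region.

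Section 11 does not use the term key secondary. The outcome it labels as the 48-week secondary endpoint is a perfusion measure: "For the secondary endpoint at 48 weeks (phase 2), a similar mixed model will be used to compare changes in global CBF".

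**The concern.** The two sections differ in unit (lesion against region) and in summary (proportion improved against change in MD or FA). The contrast in Section 11 is also not the one that randomisation protects. Stage 3 exists to assess the effect of ACZ on lesion evolution and to inform a phase 3 trial. If Section 11 is followed, the named endpoint gets no estimate. Neither the set of lesions nor the change that counts as improvement is fixed in advance, so any proportion reported later would be defined after the data had been seen.

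**Working it through.** **1. The one power figure tied to MD and FA.** Section 11 states that 50 patients give 80% power for a correlation of 0.39 between CBF and MD or FA. By Fisher's z, two-sided alpha 0.05 (sidedness is not stated, so this is an assumption):

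n = ((1.960 + 0.842) / atanh(0.39))² + 3 = (2.802 / 0.412)² + 3 = 49.3, so 50.

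With n = 50 the smallest detectable r is tanh(2.802 / √47) = 0.387, and power at r = 0.39 is 80.6%. The figure reproduces. It concerns an association between perfusion and diffusion measures. It does not concern a proportion of lesions or a difference between arms.

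**2. The planned analyses set against the endpoint.**

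| Planned item | Unit | What it estimates | Proportion of lesions improved? | Explicit week 0–24 ACZ-versus-placebo effect within lesions? |
|---|---|---|---|---|
| Section 2.2 endpoint | Lesion | Share with improved integrity | This is the target | Implied by the Stage 3 design |
| Section 11, by CBF response | Region, undefined | MD/FA change where CBF rose by more than 15% against elsewhere | No | No; groups are formed by a post-treatment response |
| Section 11, by lesion presence | White matter area, undefined | Difference in MD/FA change between two kinds of tissue | No | Not stated |
| Section 2.2, T1/T2 ratio | Not stated as lesion or patient | Rank correlation with CBF, CBV and MTT | No | No |
| Summary of Study Design, Stage 3 | Lesion volumes | Comparison between treatments | No | Volumes only; MD and FA are not in the list |

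**3. Mean change does not give the proportion.** If a share p of lesions improves by an amount a and the rest do not change, mean change is p × a. A small improvement in every lesion and a large one in a few can give the same mean. The endpoint asks for p, which needs a threshold for improvement and a lesion-level model. Section 11 has neither. Its random intercept is for the patient. Regions are treated as clusters in the regional CBF analysis, but lesions are not given a level anywhere.

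**4. The change window.** Let D be the 24-week effect of ACZ on a lesion, assumed equal in both groups. Let u₁ and u₂ be the changes that would occur without ACZ in weeks 0–24 and 24–48. The windows in Section 11 give:

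- early start, weeks 0–24: D + u₁
- delayed start, weeks 24–48: D + u₂
- difference between groups: u₁ − u₂, from which D has cancelled
- simple average of the groups: D + (u₁ + u₂)/2, which is not separated from natural evolution

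Over weeks 0–24 the randomised difference is (D + u₁) − u₁ = D. Natural evolution is not negligible here: the background states that as many as 60% of lesions resolve over six months.

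**5. Dilution.** If lesions fill a share f of a region and values are averaged over it, regional change = f × (lesion change) + (1 − f) × (change elsewhere). With no change elsewhere this is f times the lesion change. The documents give no f, no definition of region, no statement that values are averaged, and no SD for MD or FA. No loss of power can be calculated.

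**6. Power for the stated endpoint.** This cannot be computed either. It would need improvement rates on ACZ and placebo, lesions per patient and the within-patient correlation between lesions. None is given.

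**The case against.** The strongest reply is that the plan does address lesions. Section 11 compares lesion-bearing with lesion-free white matter, which partly isolates lesion tissue and guards against reading change in normal-appearing tissue as repair. Section 11 also says that the models for all outcomes include treatment group, time and their interaction, so a treatment effect in lesion areas is not excluded. Section 2.2 plans lesion counts, volumes and the T1/T2 ratio, and the Stage 3 design summary promises a comparison of imaging measures between treatments. The study is a pilot, and its primary outcome, global CBF, is unaffected.

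Much of this stands. It would be wrong to say that the plan ignores lesions or rules out a treatment comparison. But a contrast between tissue types is not a proportion of lesions, and volumes and ratios are related measures that do not estimate the diffusion endpoint. The model terms do not help if both groups enter only with their on-ACZ windows, because the group difference then compares ACZ with ACZ.

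A reader might also infer that Section 11 averages MD and FA over large brain regions, so that a lesion effect is bound to be lost. The documents do not support that. Section 11 does not define its regions or any averaging, the relaxometry objective in Section 2.2 uses regions drawn inside lesions, and dilution need not apply to the comparison by lesion presence.

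**Conclusion.** The mismatch is established from the text alone. The endpoint in Section 2.2 has no matching definition, model or power statement in Section 11. Following Section 11 leaves the proportion of improved lesions unestimated, and no randomised week 0–24 effect within lesions is explicitly planned. The cancellation in step 4 assumes the same ACZ effect in both groups and a literal reading of the stated windows. Dilution is possible if the regions are larger than lesions, but it is neither shown nor quantifiable. This should be corrected before analysis. It does not affect the primary outcome.

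**What to change.** In Section 11, define the key secondary DTI outcome as MD and FA within segmented T2 lesions present at week 0, registered to later scans, with lesions nested in patient. Report two results for weeks 0–24:

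- the ACZ-versus-placebo difference in mean within-lesion change
- the proportion of lesions improving beyond a pre-stated change, compared between arms with patient as a random effect

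For the delayed-start on-ACZ analysis (weeks 24–48), use the lesion mask from week 24. Report lesions formed after the relevant baseline scan separately, since the protocol means to evaluate new lesions as well as existing ones. Define the regions, and keep the regional MD/FA analysis and the comparison by lesion presence as supportive.

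The sequences for lesion segmentation and DTI are already acquired at every Stage 3 imaging visit, and segmentation is already planned. The cost is SAP wording and some image processing. Small lesions will give noisier MD and FA, and the improvement threshold must be fixed before unblinding.
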